6.5. Secondary Analyses

Hereinafter, the secondary analyses for Part A are described.

Secondary endpoints are functional antibody responses, fold increase in functional antibody titers and the number of subjects with seroconversion. All secondary analyses will be performed using the IMM and possibly additionally the IMMPP population, see section 5.1.

All secondary analysis endpoints will be summarized by group (i.e. by cohort) and all cohorts combined (cohort-total).

The functional antibody response will be assessed at the following time points:

P/B at day 1 (day of primary immunization, pre-dose), 7 ± 1 days and 21 ± 2 days after primary immunization and at 7 ± 3 days, 14 ± 3 days, 21 ± 4 days, 28 ± 4 days, 63 ± 7 days, 162 ± 9 , and 365 ± 14 days after the boost immunization.

6.5.1. Functional antibody response

Definition

For data from VisMederi Srl, the functional antibody response is based on the virus neutralization test (VNT). For each subject and each time point two functional antibody titers will be determined, as each sample will be measured in replicate. The functional antibody response per subject and timepoint is defined as the geometric mean of the two functional antibody titers.

Other data on functional antibody response will be presented as included in the SDTM data.

Analysis

Functional antibody titers will be summarized using descriptive statistics for all time points. Additionally, GMT with 95% CI will be presented.

The functional antibody response will be listed.

Figure: Functional antibody titers will be presented graphically displaying GMT with 95% CI at all time points.

6.5.2. Functional antibody titers fold increase

Definition

The fold increase of the functional antibody response will be calculated for all post-baseline time points as post-dose value / baseline value.

Analysis

The fold increase in functional antibody titers will be summarized using descriptive statistics for all post-baseline time points. Additionally, GMFR with 95% CI will be presented.

Functional antibody titers fold increase will be listed.

Figure: The fold increase of functional antibody titers will be presented graphically displaying GMFR with 95% CI at all time points.

6.5.3. Seroconversion

Definition

Seroconversion is defined as a minimum of 4-fold increase of functional antibody response as compared to baseline.

Analysis

The number of subjects with seroconversion will be summarized by number and percentage with 95% CI for all post-baseline time points. The denominator of the percentages will be the number of subjects with data available at the respective visit.

Seroconversion data of the functional antibody titer will be listed.

6.6. Exploratory Analyses

Exploratory analyses will be described in a separate biomarker SAP provided by BioNTech.

6.7. Further Safety Analyses

Hereinafter, the further safety analyses for Part A are described. All analyses will be performed in the SAF.

Further safety data that will be presented includes IMP compliance, clinical laboratory assessments, vital signs, and Electrocardiograms (ECGs).

6.7.1. Compliance

IMP compliance will be summarized by group (i.e. by cohort) and cohort-total.

Drug exposure will be listed.

6.7.2. Laboratory Assessments

Definition

Clinical laboratory data to be summarized includes hematology, clinical chemistry, and urinalysis and will be assessed at the time-points indicated in Table 3 of the protocol.

The following clinical laboratory variables will be assessed:

Hematology

Hemoglobin, hematocrit, red blood cell count, white blood cell count and differential (neutrophils, lymphocytes, monocytes, eosinophils, basophils), platelet count.

Clinical chemistry

Alkaline phosphatase, creatinine, ferritin, C-reactive protein, albumin, alanine aminotransferase, amylase, aspartate aminotransferase, gamma glutamyl transpeptidase, total bilirubin, blood urea nitrogen, glucose, lipase, sodium, potassium, calcium.

Follicle-stimulating hormone: Only in women who are not of childbearing potential.

Urinalysis

Dipstick: glucose, bilirubin, ketone, specific gravity (1 mL \triangleq 1 g), blood, pH, protein, urobilinogen, nitrite, and leukocytes.

Microscopic urinalysis: If warranted by dipstick results, urine sediment will be microscopically examined for presence of red blood cells, white blood cells, casts, crystals, epithelial cells, and bacteria.

All laboratory tests are classified as normal or lower or higher than reference range (abnormal). All abnormal laboratory tests will be classified by the investigator as clinically significant (CS) or not (NCS).

Abnormal lymphocytes data will be categorized as defined in table 9 in the protocol as grade 1 (mild), grade 2 (moderate), grade 3 (severe) and grade 4 (potentially life threatening).

Analysis

Clinical laboratory variables at each time-point and its change from baseline to each post-baseline time-point (for continuous variables) will be summarized using descriptive summary statistics for each parameter by group and cohort-total.

Number and percentage of subjects with low, normal and high clinical laboratory values at each time-point will be summarized for each parameter by group and cohort-total. The same table will be provided for the grading scheme (grades mild, moderate, severe and life threatening) for lymphocytes.

The number and percentage of subjects with CS abnormal, abnormal (not CS), normal and missing values will be summarized for each parameter by group and cohort-total.

Clinical laboratory values for each parameter will be summarized using shift tables from baseline to worst post-baseline value with respect to reference range values (low, normal, high) by group. Worst post-baseline might be in both directions. Each subject may be counted in the parameter high and in the parameter low category. A subject will only be counted in the normal category if

all post-baseline values are normal. If several post-baseline values are considered as worst post-baseline value, the first one is taken.

All clinical laboratory data will be presented in the data listings along with normal ranges. Abnormal clinical laboratory values will be flagged in the listing.

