#### **Clinical laboratory parameters**

The clinical laboratory parameters to be summarized and assessed are listed in Section 10.2. The scheduled time points for assessment are given in the SoA (see Section 1.3).

Clinical laboratory parameters at each time point and change from baseline to each postbaseline time point will be summarized using descriptive summary statistics for each parameter by group.

Shift tables from baseline to worst intensity grade will be provided for each laboratory parameter by group.

Additionally, the occurrence of clinically significant abnormal laboratory results within a trial subject will be analyzed using descriptive summary statistics for each parameter and visit by group.

Abnormal laboratory results will be graded using criteria based on the guidance given in US FDA Guidance for Industry "Toxicity Grading Scale for Healthy Adult and Adolescent Volunteers Enrolled in Preventive Vaccine Clinical Trials" (see Section 10.3.1.11).

Laboratory parameter results will be listed along with the normal ranges. Values that are below or above the normal ranges will be flagged.

Clinical laboratory analysis details will be described in the SAP.

Page 61 of 133 Version: 10.0 Date: 12 MAY 2021

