### Laboratory abnormalities

Laboratory abnormalities will be graded according to the grading scheme given in Table 7.

Table 7: Laboratory abnormality grading scale

	Mild (Grade 1)	Moderate (Grade 2)	Severe (Grade 3)	Potentially life- threatening (Grade 4)
Hematology				
Hemoglobin (female) - g/dL	11.0 – 12.0	9.5 – 10.9	8.0 – 9.4	<8.0
Hemoglobin (female) change from baseline value - g/dL	Any decrease – 1.5	1.6 – 2.0	2.1 – 5.0	>5.0
Hemoglobin (male) - g/dL	12.5 – 13.5	10.5 – 12.4	8.5 – 10.4	<8.5
Hemoglobin (male) change from baseline value - g/dL	Any decrease – 1.5	1.6 – 2.0	2.1 – 5.0	>5.0
WBC increase - cells/mm 	10,800 – 15,000	15,001 – 20,000	20,001 – 25,000	>25,000
WBC decrease - cells/mm 	2,500 – 3,500	1,500 – 2,499	1,000 – 1,499	<1,000
Lymphocytes decrease - cells/mm 	750 – 1,000	500 – 749	250 – 499	<250
Neutrophils decrease - cells/mm 	1,500 – 2,000	1,000 – 1,499	500 – 999	<500
Eosinophils - cells/mm 	650 – 1,500	1,501 – 5,000	>5,000	Hypereosinophilic

Page 78 of 133

Version: 10.0

Date: 12 MAY 2021

	Mild (Grade 1)	Moderate (Grade 2)	Severe (Grade 3)	Potentially life- threatening (Grade 4)
Platelets decreased - cells/mm 	125,000 - 140,000	100,000 - 124,000	25,000 – 99,000	<25,000
Chemistry				
BUN - mg/dL	23 – 26	27 – 31	>31	Requires dialysis
Creatinine - mg/dL	1.5 – 1.7	1.8 – 2.0	2.1 – 2.5	>2.5 or requires dialysis
Alkaline phosphatase - increase by factor	1.1 – 2.0x ULN	2.1 – 3.0x ULN	3.1 – 10x ULN	>10x ULN
Liver function tests – ALT, AST - increase by factor	1.1 – 2.5x ULN	2.6 – 5.0x ULN	5.1 – 10x ULN	>10x ULN
Bilirubin – when accompanied by any increase in liver function test - increase by factor	1.1 – 1.25x ULN	1.26 – 1.5x ULN	1.51 – 1.75x ULN	>1.75x ULN
Bilirubin – when liver function test is normal - increase by factor	1.1 – 1.5x ULN	1.6 – 2.0x ULN	2.0 – 3.0x ULN	>3.0x ULN

Abbreviations: ALT = alanine aminotransferase; AST = aspartate aminotransferase; BUN = blood urea nitrogen; ULN = upper limit of normal; WBC = white blood cell.

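### The SAP's laboratory shift tables use low/normal/high, so none of the 12 analytes with a grading scale gets the baseline-to-worst-grade shift that the protocol plans

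*SAP*

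**What the plan says.** Protocol 9.4.5, under clinical laboratory parameters, commits to a specific output: "Shift tables from baseline to worst intensity grade will be provided for each laboratory parameter by group". It refers grading to Protocol 10.3.1.11, which states: "Laboratory abnormalities will be graded according to the grading scheme given in Table 7". It also passes the finer points on: "Clinical laboratory analysis details will be described in the SAP".

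SAP 6.7.2 sets out these laboratory outputs:

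- descriptive statistics and change from baseline, by time-point;
- counts of low, normal and high values, by time-point;
- a graded version of that table for one analyte: "The same table will be provided for the grading scheme (grades mild, moderate, severe and life threatening) for lymphocytes";
- counts of clinically significant, not clinically significant, normal and missing values;
- "shift tables from baseline to worst post-baseline value with respect to reference range values (low, normal, high) by group";
- listings of all values with normal ranges and a flag for abnormal values. No grade is mentioned.

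The SAP version history records, for version 2, that the table by grade is confined to lymphocytes because it is most useful there. It does not mention the shift tables. The SAP introduction says that changes from the protocol are documented in section 7.1. The visible text of 7.1 mentions neither laboratory change, but its first bullet is blank in the public copy.

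**The concern.** A reference-range shift shows that a value left the normal range. A grade shift shows how far it moved. The protocol chose the second and the SAP delivers the first.

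The trial's primary objective is to describe safety and tolerability, with 12 subjects per cohort. A count of subjects by worst laboratory grade is compact at that size and easy to compare across doses. Without it, a cohort with several mild elevations and a cohort with the same number of severe ones give the same shift table.

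**Working it through.** The plan states no figure on this point. The check is a comparison of texts and a count.

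**1. Analytes that can be graded.** Inputs: Protocol 10.2 (test list) and Table 7 (scale).

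- Blood parameters: 10 haematology + 16 chemistry = 26 (FSH and urinalysis excluded).
- Analytes with a Table 7 scale: haemoglobin, WBC, lymphocytes, neutrophils, eosinophils and platelets (6), plus BUN, creatinine, alkaline phosphatase, ALT, AST and bilirubin (6) = 12.
- No scale: 26 − 12 = 14, so a grade shift is impossible for these.

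**2. What the SAP delivers for the 12.**

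- Baseline-to-worst-grade shift: 0 of 12. Lymphocytes lose it too, because their graded table is by time-point and is not a shift.
- A grade in any laboratory summary: 1 of 12 (8%), leaving 11 of 12 (92%). This second figure needs both SAP choices. The shift-table change alone does not produce it.
- Other ways of counting: with ALT and AST as one item, 10 of 11; by Table 7 row, 15 of 16.

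**3. What one cell hides.** On Table 7, ALT at 1.1 × ULN is Grade 1 and at 11 × ULN (above 10 ×) is Grade 4. Both are high in the SAP table.

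**4. Whether another output recovers the count.**

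- Clinically significant / not significant is a judgement by the investigator, not a grade.
- By-visit statistics and the lymphocyte grade table treat each of the four scheduled post-baseline draws (Visits 2, 3, 5 and 7 in Protocol Table 3) separately. They do not give each subject's worst grade.
- TEAE tables are graded but hold only what was recorded as an AE. Protocol 10.3.1.7 says that a finding documented as not clinically significant should not be recorded as one.
- Listings hold every value, but a reader would have to grade and count by hand.

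No output counts subjects per cohort by worst laboratory grade.

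**5. What full delivery needs.**

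- WBC has an increase scale and a decrease scale, so shift tables = 11 × 1 + 1 × 2 = 13.
- The haemoglobin scale headed "Hemoglobin (male) change from baseline value - g/dL", and its counterpart for women, have no baseline grade. They call for a count by worst grade, not a shift: 1 more output, 14 in all.
- Four of the 12 analytes need a derivation rule. Grade 4 is worded as hypereosinophilic for eosinophils. It depends on dialysis for BUN, and in part for creatinine.
- Bilirubin is the fourth. It has one scale "when accompanied by any increase in liver function test" and another "when liver function test is normal - increase by factor". At 1.8 × ULN it is Grade 4 on the first (above 1.75) and Grade 2 on the second (1.6–2.0). At 2.0 × ULN with normal liver tests it lies in both Grade 2 (1.6–2.0) and Grade 3 (2.0–3.0).
- The ULN bands leave gaps, for example ALT between 2.5 × and 2.6 ×, so a rounding rule is needed.

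**The case against.** The best defence has four parts.

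- **The protocol leaves laboratory detail to the SAP.** True, but the same section states the worst-grade shift tables outright. How to build them is a detail; whether to produce them is not.
- **The change was disclosed.** Partly. The version history discloses the lymphocyte restriction with a reason, and a generous reader could take it to cover any laboratory table by grade. It names neither the shift tables nor Protocol 9.4.5. A reader might infer that the departure was left out of SAP 7.1. The blank bullet there may be removed text, so the documents do not support that inference.
- **The protocol's wording cannot be met in full.** This stands: 14 of 26 blood parameters (54%) have no scale, and low/normal/high is the sensible table for them. It does not explain dropping the grade for the other 12.
- **Abnormalities that matter are graded elsewhere.** This largely stands. Protocol 10.3.1.7 requires clinically significant findings to be recorded as AEs with a grade, and the SAP tabulates TEAEs by worst grade. Listings also let a reader count by hand with 12 subjects per cohort. This limits the harm mainly to values judged not clinically significant.

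**Conclusion.** The mismatch is real and worth correcting. The planned worst-grade shift is absent for 12 of 12 gradable analytes, and 11 of 12 have no grade in any laboratory summary. The effect is on safety reporting only. Part A vaccinations are complete, no hypothesis is tested, and laboratory data are among the other safety analyses, not the primary endpoints. The counts rest on the visible text of both documents and need no outside figure.

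Two stronger readings are tempting and are not supported:

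- **That the dose-limiting toxicity assessment is weakened.** The laboratory abnormalities in Protocol 6.6.1 are the clinically significant ones, and these are recorded and graded as AEs.
- **That the SAP loses within-range haemoglobin falls which the planned shift table would have shown.** The change scale has no baseline grade, so a true shift table would not show them. Whether a given fall stays within range also depends on reference limits that the documents do not give.

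One secondary point needs only clarification. SAP 6.1.1 and 6.1.2 keep unscheduled values out of summary tables, while 6.7.2 calls a subject normal only when every post-baseline value is normal. The documents give no basis for saying how often this would matter.

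**What to change.** In SAP 6.7.2:

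1. Restore shift tables from baseline to worst grade, by group, for the 12 Table 7 analytes, with WBC in both directions and haemoglobin on the absolute scale. Give haemoglobin change as a count of subjects by worst post-baseline grade.
2. Add short derivation rules for bilirubin (concurrent liver tests, the overlap at 2.0 × ULN), the dialysis and hypereosinophilic criteria, and rounding between bands.
3. Keep low/normal/high shifts for parameters without a scale.
4. State whether the worst post-baseline value uses unscheduled values.
5. Correct the reference to protocol table 9; the scale is Table 7.

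In SAP 7.1, list any remaining departure from Protocol 9.4.5 with its reason.

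The cost is SAP wording, rules for four analytes, one rounding rule, and 13 shift tables plus one count, which can be panels of fewer outputs. No new data are needed. The main downside is many Grade 1 haemoglobin changes, because Table 7 grades any decrease; a footnote should say so.

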6.7.3. Vital Signs

Definition

Vital sign parameters to be summarized include body temperature [°C], pulse rate [bpm], respiratory rate [breaths per minute], and systolic and diastolic blood pressure [mmHg] and will be assessed at the time-points indicated in Table 3 of the protocol. Only body temperature assessed at the vital signs assessments will be shown (no body temperature assessed in the diary). Normal ranges of the vital sign parameters are given in Table 3. If a value is out of range, it is categorized as CS or not clinically significant (NCS) in the CRF.

Table 3 Normal Ranges for Vital Signs

Parameter	Range
Systolic blood pressure	90-140 mmHg
Diastolic blood pressure	<= 90 mmHg
Pulse rate	50-100 bpm
Respiration rate	8-20 breaths per minute
Temperature (where applicable)	35.5-37.5 °C

Analysis

Vital sign variables at each time-point, and its change from baseline to each post-baseline time-point will be summarized using descriptive summary statistics for each parameter by group and cohort-total.

Vital sign values for each parameter will be classified as normal/abnormal according to whether the value is within or outside of the reference range for that parameter (see Table 3). The number and percentage of subjects with CS abnormal, abnormal (not CS), normal and missing values will be summarized for each parameter by group and cohort-total.

All vital sign data will be presented in the data listings. Abnormal vital signs values and clinically significant vital sign abnormalities will be flagged in the listing.

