#### Vital signs

The vital sign parameters to be summarized and assessed are given in Section 8.2.2. The scheduled time points for assessment are given in the SoA (see Section 1.3).

Vital sign parameters at each time point and change from baseline to each post-baseline time point will be summarized using descriptive summary statistics for each parameter by group.

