## 10.3.1.1 Events meeting the AE definition

Any abnormal laboratory test results (hematology, clinical chemistry, or urinalysis)
or other safety assessments (e.g., ECG, radiological scans, vital signs
measurements), including those that worsen from baseline, and which are
considered clinically significant in the medical and scientific judgment of the
investigator, may be considered as AEs.

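### SAP Table 3 gives diastolic blood pressure no lower normal limit, so low diastolic values are tabulated as normal, left unflagged, and do not trigger the CRF significance rating

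*SAP*

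**What the plan says.** SAP 6.7.3 (Vital Signs) lists normal ranges in its Table 3. Systolic pressure is 90 to 140 mmHg, pulse rate 50 to 100 bpm, respiration rate "8-20 breaths per minute", and temperature 35.5 to 37.5 °C. Diastolic pressure has one bound only: at most 90 mmHg.

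Three rules in the same section depend on that table:

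- Classification: "Vital sign values for each parameter will be classified as normal/abnormal according to whether the value is within or outside of the reference range" for the parameter concerned.
- Rating: "If a value is out of range, it is categorized as CS or not clinically significant (NCS) in the CRF".
- Tabulation: "The number and percentage of subjects with CS abnormal, abnormal (not CS), normal and missing values will be summarized for each parameter", by cohort and for all cohorts combined. The listing flags abnormal values and clinically significant abnormalities.

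Two further displays do not depend on the ranges. One is numerical: "Vital sign variables at each time-point, and its change from baseline to each post-baseline time-point will be summarized using descriptive summary statistics". The other is the listing itself: "All vital sign data will be presented in the data listings".

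The protocol (9.4.5, Vital signs) plans only the numerical part: "Vital sign parameters at each time point and change from baseline to each post-baseline time point will be summarized using descriptive summary statistics". It gives no normal ranges. The normal/abnormal table is an addition made in the SAP.

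**The concern.** With no lower bound, a diastolic reading cannot be out of range on the low side, however low it is. The diastolic abnormal counts will consist of high values only. A reader of the table cannot tell whether low readings were absent or were counted as normal. For the other four parameters the table covers both directions, so the reader has no reason to expect diastolic pressure to differ, and the SAP does not explain the asymmetry. The laboratory section of the same SAP (6.7.2) does look both ways, with low, normal and high categories and a worst value that may lie in either direction.

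This matters because describing safety and tolerability is the primary objective, and vital signs are a planned safety summary. The schedule of activities has them taken at 1, 3 and 6 h after each immunization, when a fall in pressure after dosing could show. What is at stake is the count, by cohort and time point, of subjects with low diastolic values, in particular those not judged clinically significant.

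**Working it through.** The plan states no figure on this point, so there is none to reproduce. The check applies the Table 3 rule literally: a value is abnormal if it is below a stated lower limit or above a stated upper limit, and otherwise normal.

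| Parameter | Range in SAP Table 3 | Test value | Class under the rule |
|---|---|---|---|
| Systolic pressure | 90 to 140 mmHg | 89 | abnormal (low) |
| Pulse rate | 50 to 100 bpm | 49 | abnormal (low) |
| Respiration rate | 8 to 20 per minute | 7 | abnormal (low) |
| Temperature | 35.5 to 37.5 °C | 35.4 | abnormal (low) |
| Diastolic pressure | at most 90 mmHg | 20, 30, 40, 50, 60 | normal (all five) |
| Diastolic pressure | at most 90 mmHg | 90 | normal |
| Diastolic pressure | at most 90 mmHg | 91 | abnormal (high) |

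Diastolic pressure is the only parameter that can never be abnormal on the low side.

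The two pressure rows are classified separately. A reading of 90/40 mmHg is normal on both. A reading of 89/40 mmHg is abnormal on the systolic row and still normal on the diastolic row. The unprotected case is therefore low diastolic pressure with systolic pressure at 90 mmHg or above.

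For a diastolic value of 40 mmHg, the rules in SAP 6.7.3 then give:

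1. Class: normal.
2. CRF rating: not triggered, because the value is in range.
3. Table: counted as normal. The four categories have no place for a value that is in range but clinically significant.
4. Listing: printed, without an abnormal flag.

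The other routes by which the same value could be seen:

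- Descriptive statistics. SAP 6.1.1 includes the minimum, so the lowest value in each cohort of 12 appears at each scheduled time point. This is one extreme value; it does not say how many subjects were low. Unscheduled visits are left out of the summary tables (SAP 6.1.2).
- Listing. The value is there, but the reader has to search for it.
- Adverse events. Protocol 10.3.1.1 allows a vital-sign result to be reported as an AE if it is "considered clinically significant in the medical and scientific judgment of the" investigator, and 10.3.1.9 gives rules for vital-sign abnormalities without numerical limits. Neither is tied to SAP Table 3. Protocol 10.3.1.7 says that findings judged not clinically significant should not be recorded as AEs, and those are the findings that the abnormal-but-not-significant category exists to count.

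**The case against.** The strongest case on the other side is that the one-sided limit looks deliberate: the table uses an explicit less-than-or-equal sign, and the other four rows are intact. No passage requires a lower diastolic limit, and the protocol plans only descriptive vital-sign summaries, so no protocol analysis is lost. Low pressure has a safeguard in the systolic lower limit of 90 mmHg, and with 12 subjects per cohort the minimum is informative. All of this stands, and it narrows the point. It does not supply the missing count, and a deliberate asymmetry would still need a stated reason.

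A reader might infer that low diastolic values are never assessed for clinical significance. The documents do not support that. The investigator judges the clinical significance of vital signs for AE reporting whatever the SAP range; only the range-triggered rating in the CRF is missing. A reader might also infer that the Safety Review Committee's dose decisions were affected. The protocol has vital signs supplied to that committee, but nothing ties its review to SAP Table 3.

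The objection is also right about retrospective ratings. Vaccination was complete by 12 March 2021 (protocol 4.1), and SAP 3.0 is dated 27 April 2022. Asking investigators to rate readings more than 13 months old would produce weak evidence.

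**Conclusion.** The point holds as a minor defect in one descriptive safety table. Under the rule as written, every low diastolic value is classed as normal, is not put forward for the CRF rating, and is not flagged. The harm is limited to isolated low diastolic pressure, because a concurrent systolic value below 90 mmHg is caught on its own row and clinically significant findings have the AE route.

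How many readings are affected cannot be known: the documents give no vital-sign data, so the number could be zero or more. No primary or secondary endpoint definition depends on this table, and no hypothesis is tested in the trial.

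The conclusion rests on two assumptions: that Table 3 is applied literally, and that the CRF uses the same range. The CRF is not among the documents. If it has its own lower diastolic limit, some ratings may exist that the SAP rule does not use, and the two need to be reconciled.

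**What to change.** Add a lower diastolic limit to SAP Table 3, taken from a documented site or CRF reference range and fixed without reference to the trial data. No value is proposed here because the documents give none. If no such limit is documented, state in the SAP why the range is one-sided and add a footnote to the table saying that low diastolic values are counted as normal.

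With the limit in place, reclassify the recorded values by program, show the newly out-of-range values as abnormal (low) in the table, and flag them in the listing. Where the CRF did not collect a significance rating, show it as not rated instead of asking for one now.

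The cost is one table cell, one extra category, and a rerun of the vital-sign table and listing. The drawback is a limit set after data collection; the report should say so and name the source of the limit.
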